E.11.e Planned Exploratory Subgroup Analyses: In addition to our primary comparisons of quality of life, and functional status, we will explore whether the peer-support intervention is differentially effective in specific, identifiable subgroups of patients, including those with more or less severe depression and those who have the primary care clinician with higher versus lower level of general activity in the management of their depressed patients.

We hypothesize that: a) Benefit from PS-cCBT will not be associated with initial severity of depressive symptoms and b) Patients will benefit more from PS-cCBT than usual care if their primary care physician is less active in depression treatment.

Univariate Analyses: We will describe the frequencies of patients reporting mild, moderate, or severe depressive symptoms. We will also describe either the frequencies of patients who have primary care physicians who are more rather than less active in depression care or the mean and standard deviation of the primary care provider depression care activity measure based on the number of antidepressant fills written by the primary care provider divided by the number of patients seen in the prior FY by the provider.

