Bivariate/Multivariable Analyses: To explore the differential effectiveness of the PS-cCBT intervention among these patient subgroups, we will extend the model to include potential moderators of the intervention effect. For example, in addition to treatment group and other covariates, we will now stratify the analysis by the categories of baseline depressive symptom severity. If there is an observed differential effect (e.g., intervention effects are larger for patients with moderate or higher levels of depression symptoms than those with mild symptoms), then the differential effect of the PS-cCBT for these subgroups will be more formally assessed by adding in the main and interaction effects of the moderator (e.g., depressive symptom categories) and the intervention group. Assessment of whether the effects of PS-cCBT depend on the primary care provider's level of depression management activity will be carried out in similar fashion. Because subgroups are being considered, we may have limited power to detect differential effects of the intervention unless the interaction is large, and at the same time, due to the limited power, we may find that benefit from PS-cCBT does not depend on baseline severity of depressive symptoms. Therefore, these analyses will be exploratory and focused more on identifying trends rather than inferential testing.

E.12 Approach to Missing Data: Our initial analyses will only use observed data. We will check if missingness depends on covariates and will include those covariates in the models described above. However, we will conduct a second analysis that imputes missing data. Specifically, we will impute missing data using the method described by Lavori, Dawson, and Shera.(83) In brief, we will use logistic regression to model patients' likelihood of having specific outcome data and define strata within which outcome values are missing

at random. We will then stratify patients according to these propensities and randomly sample from the observed outcome distribution and impute values for missing data within each stratum. When data are missing for items within scales, we will use recommended imputation procedures rather than deleting patients list-wise from the analysis.

E.13 Power Analysis

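### The subgroup interaction is fitted only if the strata appear to differ, so a look that shows no difference leaves the no-moderation hypothesis without an estimate or interval

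*Combined protocol and SAP*

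**What the plan says.** Section E.11.e states one hypothesis for each moderator. Hypothesis (a), on severity, is a null: "Benefit from PS-cCBT will not be associated with initial severity of depressive symptoms". Hypothesis (b), on clinician activity, is directional: "Patients will benefit more from PS-cCBT than usual care if their primary care physician is less active in depression treatment".

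The analysis has two steps. First, "we will now stratify the analysis by the categories of baseline depressive symptom severity". Then, "If there is an observed differential effect", that effect is to be "more formally assessed by adding in the main and interaction effects of the moderator" and the treatment group. The second moderator follows the same route: dependence on the provider's level of "depression management activity will be carried out in similar fashion".

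The section also carries a caveat: "due to the limited power, we may find that benefit from PS-cCBT does not depend on baseline severity of depressive symptoms". It concludes that "these analyses will be exploratory and focused more on identifying trends rather than inferential testing".

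The plan does not say how large a stratum difference counts as observed. It gives no criterion for judging hypothesis (a), and no other section commits to fitting the interaction regardless. The section's opening remark about extending the model to cover moderators is general, and the worked example after it makes the interaction conditional.

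**The concern.** The interaction coefficient and its interval are what show how much moderation the data still allow. Under this rule they appear only when the strata already look different.

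For hypothesis (a), the outcome that agrees with the hypothesis is also the one that produces no estimate. A reader could then take the absence of a visible difference as evidence of equal benefit at all severities. Section E.3 makes that reading easy, because it already cites prior work as showing no interaction between the program and severity.

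For either moderator, an interaction that is tested has been picked because it looked large, so its nominal p-value no longer means what it says.

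**Working it through.** **Inputs.** From section E.13: 330 patients (165 per group), effect 0.4 SD, two-sided alpha 0.05, power 90%, dropout 20%. Not in the documents, and so assumed: two strata, the share f of patients in one stratum, the size of difference that counts as observed, and the variance removed by baseline adjustment.

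**1. The plan's own figure.** n per arm = 2(1.960 + 1.282)²/0.4² = 2 × 10.507/0.16 = 131.3, rounded up to 132. Then 132/0.80 = 165 per arm and 330 in total, as stated. The plan gives no power figure for an interaction.

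**2. Precision of the interaction.** For the difference D between two stratum-specific effects, in SD units, SE = √[2/(132f) + 2/(132(1−f))].

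| Split | SE | 95% half-width (1.96 × SE) | Power for a 0.4 SD interaction |
|---|---|---|---|
| 50/50 | √(4/66) = 0.246 | 0.48 | 37% |
| 30/70 | 0.269 | 0.53 | 32% |
| 20/80 | 0.308 | 0.60 | 26% |
| 50/50, adjustment removes 25% of variance | 0.246 × √0.75 = 0.213 | 0.42 | 47% |

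At 50/50 without adjustment, 80% power needs an interaction of (1.960 + 0.842) × 0.246 = 0.69 SD.

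**3. How often a real interaction is never fitted.** If a difference counts as observed when |D| > c, then P(not fitted) = Φ((c−δ)/SE) − Φ((−c−δ)/SE), where δ is the true interaction. At 50/50 without adjustment:

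- δ = 0.4, c = 0.2: Φ(−0.81) − Φ(−2.44) = 0.208 − 0.007 = 20%.
- δ = 0.4, c = 0.3: Φ(−0.41) − Φ(−2.84) = 0.342 − 0.002 = 34%.
- δ = 0.2: 45% at c = 0.2 and 64% at c = 0.3.

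If the trigger is instead that one stratum is significant and the other is not, simulation with an overall effect of 0.4 SD gives 25% not fitted at δ = 0.4.

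**4. Effect of selection when there is no interaction (50/50).** P(fitted) = 2Φ(−c/SE), which is 42% at c = 0.2 and 22% at c = 0.3. Nominal significance needs |D| > 0.48, beyond either threshold, so every significant result falls among the fitted ones. Among fitted interactions, 0.05/0.42 = 12% and 0.05/0.223 = 22% are significant at nominal 0.05. The significance-based trigger gives 10%. Counted over all trials, the rate stays at or below 5%.

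**5. Could an exclusion margin settle hypothesis (a)?** An interval of ±0.48 SD cannot lie inside ±0.4 SD. With a continuous, normally distributed moderator the equivalent half-width is 0.483 × √(2/π) = 0.385 (SE 0.197). The estimate would then have to fall within ±0.015 of zero, which happens in about 6% of trials when moderation is truly nil. With 25% of variance removed, the half-width is 0.385 × √0.75 = 0.334 and the figure is about 30%.

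**The case against.** The plan is candid. It warns of limited power, ties a possible no-dependence result to that limitation, and declares the work exploratory. A reader might infer that the plan will report a null look as confirming hypothesis (a). The documents do not say so; they only set no rule against it.

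A reader might also infer that the procedure inflates false positives. It does not: the unconditional rate stays at or below 5%, and only the p-values of tested interactions are distorted.

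Nor does the rule hide everything. Stratum results are produced unconditionally, and because the strata do not overlap, the interaction and its standard error could be derived from them if they were reported with their precision. The plan does not promise that precision for the strata, so this answers the point only in part.

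It would also go too far to say that the result will decide who is offered the program. Section F links wider implementation to improved outcomes, not to severity subgroups.

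Finally, the categories are given by way of example, and the plan allows clinician activity to be summarised by a mean and SD. The point about categorising therefore applies mainly to severity.

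What stands is the conditional rule with no threshold, applied to a hypothesis that is itself a null. An exploratory purpose is a reason to report estimates with intervals, not to withhold one.

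**Conclusion.** The point holds as a minor one, confined to the exploratory subgroup analysis. For severity, a look showing no difference ends the analysis in the hypothesised direction without the one estimate that would show how little it rules out. Across the splits and adjustment considered, that interval would be about ±0.42 to ±0.60 SD, against a planning effect of 0.4 SD. A moderation as large as the planned main effect would go unfitted in roughly a fifth to a third of trials.

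These sizes rest on 132 evaluable per arm, two strata, a normal approximation, and assumed thresholds of 0.2 to 0.3 SD. The plan mentions mild, moderate and severe categories and gives neither category shares nor a threshold, so the figures are indicative ranges.

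**What to change.** In section E.11.e, replace the conditional step with a commitment to fit the treatment-by-moderator interaction for both named moderators in all patients, whatever the strata show. Enter baseline severity as a continuous variable, and clinician activity likewise where feasible. Report each interaction with a 95% confidence interval and keep strata for display only.

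Present hypothesis (a) descriptively through its interval, and state that a non-significant or unobserved difference is not evidence of equal benefit. Do not rely on an exclusion margin: the trial is too small to meet a plausible one reliably.

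The cost is wording plus a few exploratory models: two moderators for each primary outcome examined, so up to eight for the four outcomes in section E.11.b. No new data or patients are needed. The change does not cure low power. The intervals will be wide and visibly inconclusive, which is the accurate message.

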At the time of our first in-person patient contact, we will begin our efforts to *retain* enrolled patients. During the initial assessment, patients will be asked to supply the names, phone numbers, and addresses of at least two family members, friends, or acquaintances—and give consent for staff to contact these individuals should we lose touch with the patient. As noted below, for the first 12 weeks, patients in the control condition will be receiving bi-weekly mailings giving depression self-management tips and patients in the PS-cCBT condition will be receiving peer specialist calls. These regular contacts will help maintain patients’ connection to the study. We will also send an additional mailing with study updates and logos to all patients at 18 weeks to help maintain a connection to the study and increase willingness to complete the final assessment. When needed, research staff will also check patient appointments and admissions to meet directly with patients near their scheduled assessment times.

We note that with similar procedures, we have been able to maintain a follow rate of $>85\%$ in prior RCTs even over longer time frames.

E.5 Patient Randomization

Eligible patients will be randomized to either enhanced PS-cCBT or to EUC. Random assignment will be coordinated and completed centrally at the study coordinating site to ensure that the RAs and clinical staff will not be able to determine the likely treatment assignment for the next enrollee. Randomization will be stratified by study sites, and to increase balance in prognostic factors between groups, minimization will be used for

randomization within each site. Factors to be included in minimization will include: 1) age group (≥ 55 vs. < 55), 2) gender, 3) antidepressant medication fill in prior 90 days vs. not, and 4) depression severity (PHQ-9 ≥ 15 vs. < 15) at time of baseline measures. Minimization method allows balancing on multiple factors, and we will utilize MinimPy, a free open-source, desktop minimization randomization program in this study.(61)(62)(63)

E.6 Study Groups and Intervention Description

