Threats to safety of patients in this study may also arise from the study interventions. Specifically, patients in the PS-cCBT arm may become more distressed or symptomatic through working with the cCBT modules or through their interactions with peer specialists. To mitigate this possibility, all peer specialists will be supervised by clinicians who are part of the PC-MHI team, who in turn, will work in concert with Drs. [name] and [name] who will oversee peer specialists' training and activity across study sites.

Patients' clinical status will also be systematically followed in the BTB program through the use of standardized scales (an inherent part of this clinical intervention) so that clinical worsening will be readily identified. This level of symptom monitoring is as intensive as that provided in proactive care management. If patients' symptoms are increasing significantly over time (i.e. depression scores increase >25% from baseline at more than one follow up clinical assessment point), then the supervising clinician will contact the patient and discuss their treatment progress, treatment preferences, and options for increasing the intensity of treatment.

Also, at the end of PS-cCBT participation, patients who continue with problematic symptoms will be encouraged to progress on to more intensive treatments. Please note that, PS-cCBT is not designed to “replace” more intensive and proven interventions, such as face-to-face individual CBT, but to serve as a first intervention that may provide sufficient benefit but could also serve as a “stepping-stone” to more intensive care if needed.

Potentially, patients in the study may develop suicidal ideation. Again, this will be monitored as part of the cCBT program as often as in proactive care management. The cCBT program will include information about local emergency resources as well as the Veterans Crisis Line which can provide immediate assistance. Research staff will also be available in a timely fashion and will further assess the seriousness of any emerging suicidal ideation or behaviors within 48 hours. Patients’ clinicians will also be informed and asked to follow up.

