E.11.a Analyses of Success of Randomization: We will first determine the success of the randomization process for potential prognostic factors that may affect the primary outcomes of severity of depressive symptoms and functional status, but were not considered in minimization scheme. These factors include variables such as prior hospitalization or baseline severity of anxiety symptoms. Potential differences between groups will be determined through the use of t-tests or chi-square analyses, as appropriate. When there are significant differences in the distribution of these variables, they will be included as covariates in multivariable analyses. The interpretations of final results will also be made carefully in the presence of significant baseline differences.

E.11.b Analyses Relevant to Primary Aims: Primary study analyses will determine the effectiveness of the PS-cCBT intervention in decreasing depressive symptoms (IDS-SR), improving functioning and quality of life (VR-12, Q-LESQ-SF), and increasing recovery focus (RAS) at 24 weeks post-enrollment. We will also examine the impact of the intervention on depression coping efficacy and skills, antidepressant adherence, and initiation and completion of traditional in-person psychotherapy (contingent on symptoms).

Analyses will be of two broad types, those that assess intervention effects at each assessment point (12 weeks and 24 weeks), and those that determine effects over time. Primary analysis will be based on “intent to treat” principle, with all randomized patients included in the originally randomized group, regardless of whether they have subsequently dropped from their assigned treatment group.

Univariate Analyses: In the first phase of analysis (data verification), we will examine the distribution of all study variables to assess extreme values, missing data, variances, possible coding errors, skewness and whether or how to categorize skewed data. We will then describe means ($\pm SD$) for the continuous IDS-SR, VR-12, Q-LESQ-SF, and RAS measures by study group for each assessment time for the entire sample and

for each of the study sites, separately.

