Bivariate/Multivariate Analyses: We will evaluate bivariate associations between patients' treatment condition (PS-cCBT versus EUC) and the study outcomes to determine unadjusted measures of effect. We will also examine bivariate relationships between each of the potential covariates and the outcomes, and between each of the potential covariates and intervention group to assess possible confounders. Bivariate relationships between potential covariates will also be assessed for any collinearity in subsequent analyses.

Independent (Predictor) Variables	Dependent (Outcome) Variables
Treatment Group PS-cCBT vs Usual Care Potential Covariates Demographics Baseline measures of outcome variables Psychiatric comorbidities Study Site Social Support Prior to Enrollment General Primary Care Clinician Level of Depression Treatment Activity Distance to nearest VA facility	Primary Outcome Variables IDS-SR VR-12 Q-LES-Q-SF RAS Secondary Outcomes * Depression Coping skills (DCSES, CBTSQ) Antidepressant adherence Traditional psychotherapy use (contingent on symptoms) Hope Patient activation Anxiety Suicidal Ideation

* please note some secondary outcomes may be considered mediators in other study analyses

Effects At Each Assessment Time: Comparison at 24 weeks post-enrollment will be our primary comparison, but we will also assess patient outcomes to acute effects of the PS-cCBT intervention at 12 weeks. We will first obtain unadjusted differences in the outcomes between the two study groups with its associated 95% confidence interval. Comparisons of primary outcomes (IDS-SR, VR-12, Q-LES-Q-SF, RAS) between treatment groups at each assessment time will be accomplished using multiple regression models. Multiple regression models for each outcome variables will include the baseline values of the outcome variable as covariates to adjust for baseline differences, making the model analogous to analysis of covariance. We will also include two dummy variables for three sites and adjust for additional baseline covariates that show baseline imbalances in bivariate analyses.

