Effects over time: We will next compare the effects of the PS-cCBT intervention versus EUC over time. This second set of analyses will use linear mixed-effects model with outcomes at all three assessment times as the response variable. The mixed-effects model will include patient as random intercepts to take into account the correlation of data within person over time. The model will allow the full use of all observed data despite missing outcomes at one or two assessment times and will give unbiased estimates as long as the missingness does not depend on the unobserved missing data (missing at random).

Using this model, we will be able to estimate the time-averaged effect of the intervention if the response to the intervention is immediate and lasting, or compare the rates of changes in the outcomes between the two groups if the outcomes show different trends between the study groups. Whether we compare the time-averaged effects or the rates between two groups, we will be guided by careful graphical exploration of the longitudinal data over time between the two groups. For example, if we find scores from IDS-SR to slowly decrease over time in the intervention group, but to slightly increase in the enhanced usual care group, we will model this by including a continuous time indicator (e.g., month since randomization) and a time by intervention group term in the model. The coefficient from the interaction term will estimate the difference in rates of change in outcomes between the two study groups.

E.11.c Secondary Outcomes: Analyses of secondary outcome of Depression Coping Skills and antidepressant medication adherence will proceed as outlined above for the primary outcome variables. For analyses of receipt of VA and non-VA traditional in-person psychotherapy, we will compare the percent

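### The primary week-24 regression drops patients with no week-24 score and cannot use their week-12 score; the mixed model that could use it has no pre-specified week-24 estimate

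*Combined protocol and SAP*

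**What the plan says.** - Section E.11.b, on effects at each assessment time: "Comparison at 24 weeks post-enrollment will be our primary comparison". Each assessment gets its own multiple regression, adjusted for the baseline value of the outcome, site, and baseline covariates found to be imbalanced. No week-12 outcome enters the week-24 model.
- Section E.12: "Our initial analyses will only use observed data". Covariates that predict missingness will be added; the candidate covariates tabulated in E.11.b are all baseline or pre-enrollment. A second analysis then imputes: it will "stratify patients according to these propensities and randomly sample from the observed outcome distribution".
- Section E.11.b, on effects over time: "This second set of analyses will use linear mixed-effects model". That section says the model uses all observed data and is unbiased under missing at random. Its target is a time-averaged effect or a difference in rates of change, and in choosing between them "we will be guided by careful graphical exploration of the longitudinal data over time between the two groups".
- Section E.10 schedules the primary outcome measures at baseline, week 12 and week 24.

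**The concern.** A patient seen at week 12 but not at week 24 carries information about the week-24 outcome. The analysis that decides the trial discards it. The analysis the plan itself describes as valid under the weaker missing-data assumption is secondary, and what it will estimate is not settled until data by arm have been plotted. If loss between weeks 12 and 24 depends on week-12 response differently in the two arms, the primary estimate is biased, and baseline covariates do not repair that. The sample size already allows for the lost patients, so the stake is possible bias and pre-specification, not power.

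**Working it through.** **1. The plan's own figure.** For 0.4 SD, two-sided alpha .05 and 90% power (E.13), 132 evaluable patients per arm are needed, with power 90.1%. Then 132 / 0.80 = 165 per arm, 330 in total. This reproduces the plan.

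**2. Patients left out.** 0.20 × 330 = 66. With 15% loss (E.4 reports follow-up above 85% in prior trials), 0.15 × 330 = 49.5, about 50.

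**3. Does the mixed model fix a week-24 estimate?** Suppose true differences of 0, 0.6 and 0.4 SD at baseline, week 12 and week 24. The time-averaged effect is (0.6 + 0.4)/2 = 0.50 over the two follow-up visits, or (0 + 0.6 + 0.4)/3 = 0.33 over all three, against 0.40 at week 24. The rate-of-change version, with complete data, gives a slope difference over 24 weeks of 0.40. With missing data it relies on a linear trend, and the plots decide whether it is used at all.

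**4. Size of the bias.** These inputs are assumptions, not in the documents: true effect 0.40 SD at both visits, baseline correlation .5 with each follow-up, week 12–24 correlation r of .6 or .7, and loss tied to week-12 score in one arm by a logit slope s. At s = 0.7, about 10% are missing at −1 SD and 31% at +1 SD. If a fraction p of those reaching week 12 is lost later, the first-order bias of the baseline-adjusted regression is s × p × (r − .5 × .5). Large simulations (300,000 per arm) agree closely. The two simulated values are for the two directions of dependence.

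| Loss pattern | r | First-order bias (SD) | Simulated estimate |
|---|---|---|---|
| 20%, all late, s = 0.35 | .6 | 0.35 × .20 × .35 = 0.025 | 0.375 / 0.427 |
| 20%, all late, s = 0.35 | .7 | 0.35 × .20 × .45 = 0.032 | 0.368 / 0.430 |
| 20%, all late, s = 0.7 | .6 | 0.7 × .20 × .35 = 0.049 | 0.351 / 0.450 |
| 20%, all late, s = 0.7 | .7 | 0.7 × .20 × .45 = 0.063 | 0.342 / 0.458 |
| 15%, all late, s = 0.7 | .7 | 0.7 × .15 × .45 = 0.047 | 0.357 / 0.443 |
| 20%, half lost at random before week 12, s = 0.7 | .7 | 0.7 × (.10/.90) × .45 = 0.035 | 0.370 / 0.431 |
| 20%, all late, same slope in both arms | .6–.7 | cancels: 0 | 0.399 to 0.403 |
| 20%, all before week 12 | .6–.7 | no late loss: 0 | 0.398 to 0.404 |

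In the late-loss cases, a week-24 contrast that uses week-12 scores gives 0.40.

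**5. What the bias does to the test.** With baseline adjustment and 132 per arm, SE = √(2 × 0.75 / 132) = 0.107. Power is 96% at 0.40, 93% at 0.37 and 89% at 0.34. With no true effect, a bias of 0.03 or 0.06 SD (0.3 or 0.6 SE) raises the 5% false-positive rate to about 6% or 9%.

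**6. What week-12 scores cannot repair.** If loss depends on the unseen week-24 score (s = 0.7, one arm), the observed-data regression gives about 0.30 or 0.50, and the model using week-12 scores 0.32 to 0.34 or 0.46 to 0.48. Only part of the bias is removed.

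**The case against.** The strongest case against is that nothing in the documents points to arm-specific loss.

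- A reader might infer it from section E.8.a, where "at the end of PS-cCBT participation, patients who continue with problematic symptoms will be encouraged to progress on to more intensive treatments". That concerns moving to other care, not leaving follow-up, and section E.11.c goes on to study psychotherapy started between weeks 12 and 24 in both arms. Table 3 notifies the primary care clinician of clinical worsening at 12 and 24 weeks in both arms, and retention contact is shared: an "additional mailing with study updates and logos to all patients at 18 weeks". This stands, so the bias is a possibility to guard against, not a prediction.
- A reader might also infer that the plan contradicts its intent-to-treat statement, "with all randomized patients included in the originally randomized group". Read to its end, that sentence is about patients who leave their assigned treatment. It says to analyse by assigned arm and does not clearly promise a value for every missing score. No contradiction is claimed.
- The imputed analysis does bring the missing patients back. It remains a second analysis, and E.12 does not say whether week-12 score informs it. The method is given in brief by citation and may settle that, so this is missing detail and not an error.
- Timing matters. The one place that times dropout (E.13, psychotherapy power) assumes 20% lost by week 12. If all loss is that early, the bias described here is absent and week-12 scores cannot help.

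These points limit the size of the concern. They do not supply a pre-specified week-24 estimate that uses the week-12 data.

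**Conclusion.** The point holds as a gap in the primary analysis and its pre-specification. The week-24 regression leaves out patients without a week-24 score and ignores their week-12 score, and neither secondary analysis is stated in a form that gives a fixed week-24 estimate using that score. The bias is conditional: none under equal dependence or early loss; about 0.02 to 0.06 SD on 0.40, in either direction, if late loss depends on week-12 score in one arm only; about 0.03 SD if half the loss is early. Opposite dependence in the two arms would roughly double the late-loss figures, but nothing in the documents motivates it. All slopes, correlations and timings are assumptions. The sample size is sound. This is an inexpensive improvement worth making, not a flaw that undermines the trial.

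**What to change.** Before any data by arm are seen, pre-specify as primary the week-24 treatment contrast from a mixed model with weeks 12 and 24 as responses, categorical time by treatment, baseline score by time, site, and an unstructured covariance. This modifies the planned mixed model: baseline moves from response to covariate, time becomes categorical, and the random intercept is replaced, so that unequal variances at the two visits do no harm.

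Keep the observed-data regression and the planned imputation as supportive analyses. Add a delta-shift sensitivity analysis for losses that week-12 scores cannot correct, and report losses before and after week 12 by arm.

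The cost is SAP wording and a little more programming; no patients or visits are added. The price is reliance on missing at random given week 12, and patients with neither follow-up score still add nothing to the contrast. Precision gains are small: under random dropout, with an assumed partial correlation of .4 to .7 and 50% to 100% of the missing having a week-12 score, power rises from 90.1% to about 90.6–92.8%.
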